9.4 Buccal Swab Samples

9.4.1 Collection, Processing, and Shipping

1. Ideally have the patient rinse mouth out with water immediately prior to sample collection at least one hour after eating, drinking, or brushing teeth
2. Pull open the package from one end
3. Remove the swab from the tube, taking care not to touch the white swab head with your fingers
4. Insert the swab into your mouth and rub firmly against the inside of your cheek or underneath lower and upper lip. For standard DNA collection, rub for 1 minute and in all cases, for a minimum of 20 sections. Please use reasonable, firm, solid pressure
5. Slide the plastic cap over the swab handle with the flat side of the cap facing upwards and the swab facing downwards
6. Insert the swab into the clear plastic tube and push the cap into place- Next, hold the cap while pulling the swab handle outwards to release the swab material into the tube
7. Close the cap by pushing the stopper fully into the cap ensuring the stopper is flush with the cap- The tube is now completely sealed
8. Mail same day, ambient to the lead site for processing. The caps can be placed in an envelope or other container with the trial number, patient study number (if registered), date of birth, site name, collection date and time
9. Two swabs should be used for each patient to ensure adequate sample for analysis

CONFIDENTIAL

This document is confidential. Do not disclose or use except as authorized.

10. STUDY CALENDAR

Screening evaluations are to be conducted within 28 days of registration. Imaging assessments that are completed within 6 weeks of registration need not be repeated at screening. If a patient had a bone marrow core biopsy done within 6 weeks of registration, a bone marrow aspirate sample need only be collected for baseline and research purposes. Baseline assessments are to be conducted on C1D1 of initial therapy and should be considered separate from screening evaluations. If screening assessments are performed within 7 days of C1D1, disease assessments (SPEP, UPEP, Immunofixation, Free light chain assay, quantitative immunoglobulins) do not need to be repeated. Lab values that are used to prove eligibility for patients with progressive (evolving) smoldering myeloma do not need to be within the 21 day window, but screening values will need to be established in window. All assessments must be performed prior to administration of any study medication. See below for detailed scheduled of assessments. Study medications will be administered according to the schedule and guidelines outlined in Section 5.

	Pre-registration		Cycles 1-12 (28 days) ³				Follow-Up
Tests and procedures	≤ 28 days prior to registration	≤ 21 days prior to registration	Day 1 of cycles 1-6 ¹	Day 1 of cycles 7-12	Cycle 7 Day 1 and to confirm CR ⁸	End of Treatment ¹⁸	Every 3 Months ¹¹
History and exam, height, weight. Performance Status	X		X	X		X	X
Response Assessment ¹⁷			X	X		X	X
Toxicity Notation			X	X		X	
Hematology group (WBC w/ diff, PLT, Hgb, ANC)		X	X	X		X	X
Chemistry ⁴		X	X	X		X	X
Direct & total bilirubin ²		X	X	X		X	
Free light chain assay		X	X	X		X	X
Serum and Urine Immunofixation (SPEP and UPEP) with quantitative immunoglobulins ⁹		X	X	X		X	X
β2M, CRP, LDH ¹⁶		X	X	X		X	
TSH, Free T4, Free T3		X	X	X		X	
Metastatic Bone Survey and Spine MRI OR PET/CT only ¹⁰	X					X	
EKG ¹⁵		X				X	
Serum pregnancy test ¹²		X					
Unilateral bone marrow aspirate and biopsy ⁵	X				X	X	
Research bone marrow aspirate ⁶	X ⁵				X ⁶	X ⁶	
Research Blood ⁷	X ⁷		X ⁷	X ⁷	X ⁷	X ⁷	
Buccal Swab ¹³	X						

1- Cycle 1, Day 1 laboratory values need to meet eligibility criteria

2- Direct bilirubin to be obtained if total bilirubin is abnormal.

3- Scheduling allows for +/- 7 days all cycles.

4- Chemistry includes sodium, potassium, chloride, bicarbonate, bun, creatinine, calcium, glucose, albumin, ALT (SGPT), total protein, AST (SGOT), total bilirubin, magnesium, and phosphorus.

5- A bone marrow biopsy is required within 6 weeks of registration. A bone marrow aspirate for clinical and research purposes is required pre-treatment and may be performed up to 28 days prior to registration. Both core and aspirate are required any time during the course of the study to confirm CR, and is also required at C7D1

6- Research bone marrow aspirate and biopsy at the same time as clinically indicated bone marrow biopsy and to confirm response.

CONFIDENTIAL

This document is confidential. Do not disclose or use except as authorized.

Local Protocol #: 16-242

Version Date: 23 January 2018

7- Peripheral blood samples for correlative studies may be done at any time pre-treatment, though baseline and C1D1 samples should be considered separate time points.

8-If C7D1 or confirmation of response BM aspirate and core biopsy was performed within 3 weeks of either timepoint, the procedure need not be repeated. At minimum, an aspirate sample is required

9- Disease assessment/response assessment is required each Day 1 starting with C2-If the participant's disease response is not followed primarily via a UPEP (24 hour urine collection) and Urine immunofixation, these tests may be done only at screening, end of treatment, and every 3 months during treatment.

10-A CD of scans at screening and end of treatment is required to be sent to the lead site for central review. Screening scans should be sent with the eligibility packet to the lead site- This requirement includes a full body skeletal survey in addition to spinal MRI OR the patient may have only a low dose PET CT

11- Follow-up should occur every 3 months (+/- 14 days) for up to 3 years after end of treatment.

12- Women of child-bearing potential must abide by revlimid REMS procedures and may require additional pregnancy testing as described in section 3.1.7.

13- Buccal swab may be collected at any time throughout the study but should be collected pre treatment on C1D1

14- Thyroid labs are required at screening, C3D1, C6D1 and every 3 cycles thereafter, at end of treatment, and at any time that it is clinically indicated

15- Alert Overall PI immediately if there is concern for cardiac toxicity (At minimum, the following should be performed: cardiology consult, EKG, echocardiogram, and labs CPK and troponin; refer to section 6.2.7 for more details)

16- B2M, CRP, and LDH are required at screening, C3D1, C6D1 and every 3 cycles thereafter, at end of treatment, and at any time that it is clinically indicated

17- A disease response assessment will be required at every Day 1 starting with Cycle 2, end of treatment, and every follow up visit (q3 months) until completion, withdrawal, disease progression, subsequent therapy or death

18- All end of treatment assessments will be performed within 14 days from the date that the decision to end treatment was made by the study team

11. MEASUREMENT OF EFFECT

11.1 Development of symptomatic disease

In this study, the final endpoint is development of symptomatic MM that requires therapy.

This is defined as one of the following criteria (≥ 1 CRAB Criterion and Myeloma Defining Events ≥ 1 MDE):

- Increased calcium levels (corrected serum calcium >0.25 mmol/dL above the upper limit of normal or >2.75 mmol/dL) due to myeloma
- Renal insufficiency (attributable to myeloma);
- Anemia (Hb 2g/dL below the lower limit of normal or <10 g/dL) due to myeloma
- Bone lesions (lytic lesions or generalized osteoporosis with compression fractures)
- Myeloma Defining Events (MDE) as follows:
 - Clonal bone marrow plasma cell percentage $\geq 60\%$ ⁷
 - An abnormal FLC-ratio ≥ 100 (involved kappa) or <0.01 (involved lambda)⁸
 - 2 or more focal lesions on MRI or PET-CT studies^{9,10}

For measurement of response:

The disease response will be assessed using criteria based on the International Myeloma Working Group Uniform Response Criteria in Section 11.2.2.1 or FreeLite™ Disease Response Criteria in Section 11.2.2.2.

Disease response by the Modified EBMT Response Criteria in Section 11.3.2.3 will also be collected on participants as a secondary measure.

The same method of assessment and technique should be used for disease measurement at baseline and during follow-up. Disease response should be confirmed by two consecutive assessments.

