Study Population: SELECT INCLUSION CRITERIA 
• Age \geq 18 years.• Must meet criteria of high risk smoldering MM as described with one of the below criteria:
○ Bone marrow clonal plasma cells \geq 10% and any one or more of the following:
▪ Serum M protein \geq 3.0g/dL▪ IgA SMM▪ Immunoparesis with reduction of two uninvolved immunoglobulin isotypes▪ Serum involved/uninvolved free light chain ratio \geq 8 (but less than	

CONFIDENTIAL

This document is confidential. Do not disclose or use except as authorized.

100)

- Progressive increase in M protein level (Evolving type of SMM)†
- Bone marrow clonal plasma cells 50-60%
- Abnormal plasma cell immunophenotype ($\geq 95\%$ of bone marrow plasma cells are clonal) and reduction of one or more uninvolved immunoglobulin isotypes

* All patients should have four or six color flow cytometry performed on the baseline bone marrow sample, as feasible. Patients evaluated for eligibility by Spanish Criteria must have their result confirmed by four color flow cytometry. If four or six color flow cytometry is not available at the site, the baseline bone marrow must be sent to Dana-Farber Cancer Institute to confirm eligibility prior to enrollment.

- High risk cytogenetics or FISH including t (4;14) or del 17p or 1q gain
- Increased circulating plasma cells
- MRI with diffuse abnormalities or 1 focal lesion
- PET-CT with focal lesion with increased uptake without underlying osteolytic bone destruction

† Increase in serum monoclonal protein by $\geq 10\%$ on two successive evaluations within a 6 month period

- No evidence of CRAB criteria* or new criteria of active MM which including the following:
 - Increased calcium levels (corrected serum calcium >0.25 mmol/dL {1mg/dL} above the upper limit of normal or >2.75 mmol/dL {11mg/dL});
 - Renal insufficiency (attributable to myeloma);
 - Anemia (Hb 2g/dL below the lower limit of normal or <10 g/dL);
 - Bone lesions (lytic lesions or generalized osteoporosis with compression fractures)
 - No evidence of the following new criteria for active MM including the following: Bone marrow plasma cells $\geq 60\%$, Serum involved/uninvolved FLC ratio $\geq 100^*$, and MRI with more than one focal lesion (*except for light chain smoldering MM)

* Participants with CRAB criteria that are attributable to conditions other than the disease under study may be eligible

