2.4 Definition of SMM and MM

The diagnosis of smoldering (asymptomatic) multiple myeloma (SMM)^{38,39} is based on:

- Serum monoclonal protein (IgG, IgM, IgD or IgA) ≥ 3 g/dL or urinary monoclonal protein ≥ 500 mg per 24 h and/or clonal bone marrow plasma cells (BPMC) 10–60%.
- Absence of myeloma defining events or amyloidosis
- No evidence of the following CRAB criteria or other Myeloma defining events (MDE):
 - Increased calcium levels (corrected serum **calcium** >0.25 mmol/dL above the upper limit of normal or >2.75 mmol/dL) related to MM
 - **Renal** insufficiency (attributable to MM)
 - **Anemia** (Hb 2g/dL below the lower limit of normal or <10 g/dL) related to MM
 - **Bone** lesions (lytic lesions or generalized osteoporosis with compression fractures)

New MDE criteria that indicates overt MM and not SMM^{38,39}

The following criteria are now incorporated with the CRAB criteria to indicate that patients meet criteria for therapy as symptomatic or overt MM:

- Bone marrow plasma cells $>60\%$
- Serum involved/uninvolved FLC ratio ≥ 100 mg/L, provided the absolute level of the involved free light chain is at least 100 mg/L and repeated twice (except for monoclonal light chain smoldering MM and for those with stable serum light chains for 6 months.)
- MRI with two or more focal lesion that is at least 5 mm or greater in size

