3.2 Exclusion Criteria

3.2.1 No evidence of CRAB criteria* or new criteria of active MM which including the following:

- Increased calcium levels (corrected serum calcium >0.25 mmol/dL $\{>1\text{mg/dL}\}$ above the upper limit of normal or >2.75 mmol/dL $\{11\text{mg/dL}\}$) related to MM
- Renal insufficiency (attributable to MM)
- Anemia (Hb 2g/dL below the lower limit of normal or $<10\text{g/dL}$) related to MM
- Bone lesions (lytic lesions or generalized osteoporosis with compression fractures)
- Bone marrow plasma cells $>60\%$
- Serum involved/uninvolved FLC ratio ≥ 100 , provided the absolute level of the involved free light chain is at least 100 mg/L and repeated twice (light chain smoldering myeloma as described in section 2.4 is not an exclusion criteria).
- MRI with two or more focal lesions that are at least 5 mm or greater in size

**Participants with CRAB criteria that are attributable to conditions other than the disease under study may be eligible*

3.2.2 Other concurrent chemotherapy, immunotherapy, radiotherapy, or any ancillary therapy considered investigational. Prior therapy with bisphosphonate is allowed. Prior therapy for smoldering myeloma MM may not be an exclusion criterion, discussion with Principal Investigator must occur before enrolling patients with prior treatments. Prior radiation therapy to a solitary plasmacytoma is allowed. Patients who received prior therapy due to being incorrectly diagnosed as having overt multiple myeloma may not be excluded after discussion with the overall PI.

3.2.3 Serious medical or psychiatric illness likely to interfere with participation in this clinical study.

3.2.4 Diagnosed or treated for another malignancy within 2 years of enrollment, with the exception of complete resection of basal cell carcinoma or squamous cell carcinoma of the skin, an in situ malignancy, or low-risk prostate cancer after curative therapy.

3.2.5 Uncontrolled intercurrent illness including, but not limited to, ongoing or active infection, symptomatic congestive heart failure, unstable angina pectoris, cardiac arrhythmia, or psychiatric illness/social situations that would limit compliance with study requirements.

CONFIDENTIAL

This document is confidential. Do not disclose or use except as authorized.

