Stable Disease (SD)	Not meeting criteria for CR, VGPR, PR or progressive disease. This is not recommended as an indicator of response; stability of disease is best described by providing the time to progression estimates.
Progressive Disease (PD)	$> 25\%$ increase of serum M-protein (which must also be an absolute increase of ≥ 0.5 g/dL) and/or urine M-protein (which must also be an absolute increase of ≥ 200 mg/24hr). If serum and urine M-protein are unmeasurable, there must be an absolute increase of ≥ 10 mg/dL between involved and uninvolved FLC levels. PD is also measured by an absolute increase in bone marrow plasma cells $\geq 10\%$. In addition to the above listed criteria, progression may also be measured by a definite development of new bone lesions or soft tissue plasmacytomas or definite increase in the size of existing bone lesions or soft tissue plasmacytomas or development of hypercalcemia (corrected serum calcium ≥ 11.5 mg/dL or 2.65 mmol/L) that can be attributed solely to the plasma cell proliferative disorder.

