Minimal response (MR)	
MR included participants in whom some, but not all, criteria for PR were fulfilled, providing the remaining criteria satisfied the requirements for MR. Required all of the following:
 
$\geq 25\%$ to 49% reduction in the level of serum monoclonal protein for at least two determinations six weeks apart.
 
If present, a ≥ 50 to 89% reduction in 24-hour light chain excretion, which still exceeds 200 mg/24 h, for at least two determinations six weeks apart.
 
$\geq 25\text{--}49\%$ reduction in the size of plasmacytomas (by clinical or radiographic examination) for at least six weeks.
 
No increase in size or number of lytic bone lesions (development of compression fracture does not exclude response).^c

No change (NC)	Not meeting the criteria for MR or PD.
Progressive disease (PD) (for participants not in CR)	
Requires one or more of the following:
 
$>25\%$ increase^d in the level of serum monoclonal paraprotein, which must also be an absolute increase of at least 5 g/L and confirmed on a repeat investigation.
 
$>25\%$ increase^d in 24-hour urinary light chain excretion, which must also be an absolute increase of at least 200 mg/24 h and confirmed on a repeat investigation.
 
$>25\%$ increase^d in plasma cells in a bone marrow aspirate or on trephine biopsy, which must also be an absolute increase of at least 10%.
 
Definite increase in the size of existing lytic bone lesions or soft tissue plasmacytomas.
 
Development of new bone lesions or soft tissue plasmacytomas (not including compression fracture).
 
Development of hypercalcemia (corrected serum calcium >11.5 mg/dL or 2.8 mmol/L not attributable to any other cause).

CONFIDENTIAL

This document is confidential. Do not disclose or use except as authorized.

	
Required at least one of the following:
 
Reappearance of serum or urinary paraprotein on immunofixation or routine electrophoresis confirmed by at least one follow-up and excluding oligoclonal immune reconstitution.
 
Relapse from CR
 
≥5% plasma cells in the bone marrow aspirate or biopsy.
 
Development of new lytic bone lesions or soft tissue plasmacytomas or definite increase in the size of residual bone lesions (not including compression fracture).
 
Development of hypercalcemia (corrected serum calcium >11.5 mg/dL or 2.8 mmol/L not attributable to any other cause)^e.

--	---

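### Calcium limits are printed in mmol/dL in four places, including the endpoint definition, and the two progression tables pair 11.5 mg/dL with mmol/L values that do not equal it

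*Combined protocol and SAP*

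**What the plan says.** Corrected serum calcium appears as a limit in six places.

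- **Section 11.1** introduces its list with "In this study, the final endpoint is development of symptomatic MM that requires therapy". The calcium item is a rise of more than 0.25 "mmol/dL above the upper limit of normal or >2.75 mmol/dL) due to myeloma". No mg/dL figure is given.
- **Section 2.4** has the same two limits, also without mg/dL figures: "mmol/dL above the upper limit of normal or >2.75 mmol/dL) related to MM".
- **The Protocol Summary** prints the same limits with mg/dL values in braces: 0.25 "mmol/dL {1mg/dL} above the upper limit of normal" for the first, and for the second "above the upper limit of normal or >2.75 mmol/dL {11mg/dL".
- **Section 3.2.1** has the same wording, "above the upper limit of normal or >2.75 mmol/dL", again with 1 and 11 mg/dL in braces.
- **Section 11.2.2.1 (IMWG), progressive-disease row**, sets hypercalcemia at 11.5 "mg/dL or 2.65 mmol/L) that can be attributed solely to the plasma cell proliferative disorder".
- **Section 11.2.2.3 (modified EBMT)** sets it at 11.5 "mg/dL or 2.8 mmol/L not attributable to any other cause", both in the progressive-disease row and in the row for relapse from complete response. Section 11.1 describes the EBMT criteria as a secondary measure.

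**The concern.** There are two separate faults. The first is the unit: laboratories report calcium in mmol/L or mg/dL, and a limit in mmol/dL is ten times the same number in mmol/L. The second is that both response tables offer a mg/dL value and a mmol/L value as alternatives for one limit, yet the two values are different calcium levels. The two tables also give different mmol/L partners for the same 11.5 mg/dL.

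These are working definitions and not background text. Hypercalcemia is one of the CRAB events that make up symptomatic myeloma in 11.1, and it is one route to progressive disease in the response tables. Calcium is in the chemistry panel on Day 1 of every cycle, at end of treatment and at each three-monthly follow-up visit (section 10, note 4), so the criterion is applied repeatedly. Section 11.2.6 plans no central review of response, so no stated step would bring different readings at different sites into line.

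**Working it through.** **Inputs.** The limits are those listed above. The conversion factor follows from the protocol's own pairs once the unit is read as mmol/L: 11 / 2.75 = 4.0 and 1 / 0.25 = 4.0 mg/dL per mmol/L. The molar mass of calcium (40.078 g/mol, a physical constant not in the documents) gives 4.008, so the two agree. Also, 1 mmol/dL = 10 mmol/L.

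**Step 1: reproduce the protocol's mg/dL values.** Read in mmol/L, 2.75 × 4.0 = 11.0 mg/dL and 0.25 × 4.0 = 1.0 mg/dL. These are the values in braces in the Protocol Summary and 3.2.1, so mmol/L is the unit that fits.

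**Step 2: the limits as printed in mmol/dL.**

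- Absolute limit: 2.75 mmol/dL = 27.5 mmol/L; 27.5 × 4.0 = 110 mg/dL, against 11 mg/dL in braces.
- ULN limit: 0.25 mmol/dL = 2.5 mmol/L; 2.5 × 4.0 = 10 mg/dL above ULN, against 1 mg/dL in braces.
- The documents give no ULN. With an assumed ULN of 10.0 to 10.5 mg/dL, the second limit would trigger at 20.0 to 20.5 mg/dL as printed, against 11.0 to 11.5 mg/dL with the value in braces. That is about 1.8 times the level intended.

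**Step 3: the table pairs.** By molar mass, 11.5 / 4.008 = 2.87 mmol/L; by the protocol's own factor, 11.5 / 4.0 = 2.875.

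| Row | Stated pair | mmol/L value in mg/dL | Shortfall from 11.5 mg/dL |
|---|---|---|---|
| IMWG PD (11.2.2.1) | 11.5 mg/dL or 2.65 mmol/L | 2.65 × 4.0 = 10.6 | 0.9 mg/dL |
| Modified EBMT PD and relapse (11.2.2.3) | 11.5 mg/dL or 2.8 mmol/L | 2.8 × 4.0 = 11.2 | 0.3 mg/dL |

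Against 2.87 mmol/L, 2.65 is about 7.6% low and 2.8 about 2.4% low. Rounding explains neither, since 2.87 rounds to 2.9. The tables differ from each other by 2.8 − 2.65 = 0.15 mmol/L, or 0.6 mg/dL.

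**Step 4: consequence for one patient.** Take a myeloma-attributed calcium of 10.8 mg/dL, which is 10.8 / 4.0 = 2.70 mmol/L. Under the IMWG row it is progression by the mmol/L figure (2.70 is above 2.65) and not by the mg/dL figure (10.8 is below 11.5). The same holds from 10.6 to just under 11.5 mg/dL. The order relative to 11.1, read in mmol/L, also flips: the IMWG row is looser than 11.1 in mmol/L (2.65 against 2.75) and stricter in mg/dL (11.5 against 11).

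**Step 5: what does not change.** The rule of 24 or more of 39 gives an exact type I error of 0.0998 at a true rate of 50% and power of 0.906 at 70%, as section 13.1 states. Calcium limits do not enter that calculation.

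**The case against.** The strongest reply is that this is an editorial slip which the protocol itself resolves. Two of the four places print 1 and 11 mg/dL, and no one would wait for a calcium of 110 mg/dL. That stands as to intent: sites would probably apply 11 mg/dL. It does not remove the need for correction, because 11.1, where the event is adjudicated, lacks that cue. Nor does it touch the table pairs, where nothing in the text says which of the two values governs.

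Three stronger readings are tempting, and the documents do not support them.

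- *The 11.1 calcium criterion can never be met.* This fits the absolute limit only. The two limits are alternatives, and the ULN limit as printed falls at about 20 mg/dL under the assumed ULN range, which is extreme but not strictly out of reach.
- *Several competing cut-offs govern the primary event.* Section 11.1 separates the final endpoint from the criteria for measuring response, and the EBMT table is a secondary measure. Whether the IMWG row also feeds the 2-year progression-free rate is not settled in section 13 and is a separate question. A response table may also legitimately use a different limit from 11.1; the error is only that its own two figures disagree.
- *The error could overturn the 24-of-39 decision.* A single reclassified patient would matter if the count fell exactly at the boundary, but nothing in the documents shows that this is likely. The patient would need a calcium in the affected range, attributed to myeloma, with no earlier event on M-protein, marrow, bone, renal function or hemoglobin.

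It can also be said that accrual ended in September 2017 (section 1.1). Follow-up continues for up to three years after therapy (section 5.6), so the definitions in this January 2018 version can still be applied.

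**Conclusion.** The thresholds are wrong as printed. The unit in 2.4, 3.2.1, 11.1 and the Protocol Summary is off by a factor of ten, and the protocol's own mg/dL values show it. In the tables, the IMWG pair is inconsistent by 0.9 mg/dL and the EBMT pair by 0.3 mg/dL. The IMWG mismatch matters more, because it makes classification between 10.6 and 11.5 mg/dL depend on the reporting unit.

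The practical effect is probably small: calcium is one of several progression criteria. The number of patients affected cannot be derived from the documents. The conversions rest on the protocol's own factor, confirmed by the molar mass. Only the 20 mg/dL figure depends on an assumption, the ULN of 10.0 to 10.5 mg/dL. The correction should be made because it is cheap and concerns endpoint and progression definitions.

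**What to change.** 1. Change mmol/dL to mmol/L for calcium in the Protocol Summary and in sections 2.4, 3.2.1 and 11.1.
2. Add the protocol's own equivalents, 1 and 11 mg/dL, to sections 2.4 and 11.1. The Protocol Summary and 3.2.1 already have them.
3. In the IMWG progressive-disease row and in both modified EBMT rows, reconcile the mg/dL and mmol/L figures so that each pair expresses the same level. The sponsor decides which threshold applies. Simply pointing the tables to the 11.1 limit would change their threshold and goes beyond a unit correction.

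The cost is a few words in an amendment. Design, sample size, visit schedule and data collection are unaffected. If any calcium-based progression has already been recorded, its source value should be checked against the reconciled limits.

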1. OBJECTIVES

Smoldering Multiple Myeloma (SMM) is a heterogeneous disease entity that includes patients who have a disease burden that is higher than that in patients with MGUS but who are not yet symptomatic¹. The term SMM was first described by Greipp and Kyle et al in 1980² and was followed by many other descriptions terming it indolent MM³, or Durie Salmon Stage I⁴. It was not until 2003 that the International Myeloma Working Group (IMWG) described the exact definition of this disease. SMM was defined as serum M-protein ≥ 3 g/L and/or $\geq 10\%$ monoclonal plasma cells in the bone marrow (BM), Table 1^{5,6}. While the incidence and prevalence of SMM in the population is not well defined, it has been estimated to represent approximately 8% to 20% of patients within the MM spectrum¹.

Most recently, the IMWG further re-defined the group of patients who meet criteria for treatment and included asymptomatic SMM patients who are likely going to have end-organ damage in the near future, previously defined as “ultra-high risk smoldering myeloma”. These include patients with bone marrow plasmacytosis $\geq 60\%$ ⁷; an abnormal FLC-ratio ≥ 100 (involved kappa) or <0.01 (involved lambda)⁸; and/or 2 or more focal bone marrow lesions detected by functional imaging including PET-CT and/or MRI^{9,10}. These patients should therefore not be considered SMM anymore but rather re-defined as patients with myeloma-defining events that require therapy.

The overall risk of progression of SMM is 10% per year for the first 5 years and 3% per year for the next 5 years¹¹. The most common factors used to stratify patients with SMM are the Mayo Clinic criteria^{11,12} and the Spanish PETHEMA criteria¹³. The Mayo Clinic criteria are based on the tumor burden defined by the serum protein level (by serum protein electrophoresis or light chain ratio) or by the percent bone marrow plasma cell involvement (see Table 2)^{11,12}, leading to risks of progression at 5 years of 25% for low risk, 51% for intermediate risk and 76% for high risk individuals who have 1, 2 or 3 risk factors respectively^{11,12}. The risk stratification of the PETHEMA group is based on identifying the number of clonal plasma cells in the bone marrow by flow cytometry ($\geq 95\%$ ratio of abnormal neoplastic plasma cells to normal plasma cells) and reduction of uninvolved immunoglobulins, with 5 year-risk of progression being 4%, 46%, and 72% for patients with 0, 1 or 2 risk factors, respectively¹³.

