The paradigm of therapy in Smoldering Multiple Myeloma (SMM) is changing as we develop better therapeutic agents that prevent end organ damage and improve survival of patients with multiple myeloma (MM)¹⁴⁻¹⁶. Indeed, recent studies of a phase III trial of lenalidomide and dexamethasone versus placebo showed improved response, progression free survival and overall survival in patients with high risk smoldering MM compared to placebo control¹⁷. Therefore, there is a need to examine novel therapeutic combinations in patients with high risk smoldering MM.

Our overarching hypothesis is that early therapeutic interventions in patients with smoldering MM will prevent/delay progression to overt MM. We will examine the *in vivo* activity and safety of nivolumab and lenalidomide in patients with high-risk SMM.

CONFIDENTIAL

This document is confidential. Do not disclose or use except as authorized.

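### Section 11.1 lists endpoint criteria that some eligible patients can already meet at entry, with no baseline rule; separately, one FreeLite partial-response branch cannot be met

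*Combined protocol and SAP*

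**What the plan says.** Section 11.1 names the event: "In this study, the final endpoint is development of symptomatic MM that requires therapy". It is met by one of a list of criteria: the CRAB items, plus three myeloma-defining events (MDEs). The MDEs are marrow plasma cells of 60% or more, an FLC ratio of 100 or more or its reciprocal ("involved kappa) or <0.01 (involved lambda"), and "2 or more focal lesions on MRI or PET-CT studies". A parenthesis beside the list joins the two families with an and: "CRAB Criterion and Myeloma Defining Events".

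The entry text is narrower on each MDE:

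- **FLC ratio.** Section 2.4 requires an involved chain of at least 100 mg/L, repeated twice, and makes an exception: "except for monoclonal light chain smoldering MM and for those with stable serum light chains for 6 months". Section 3.2.1 keeps the 100 mg/L and repeat conditions and exempts light-chain smoldering disease. Section 3.1.2 says such patients are not excluded, and the Protocol Summary also carries the light-chain exception ("MRI with more than one focal lesion (*except for light chain smoldering MM", where the asterisk belongs to the FLC ratio).
- **Marrow.** Section 3.1.2 admits up to and including 60%, and 3.2.1 excludes only above 60%. The Summary puts 60% itself among the criteria for active disease.
- **Focal lesions.** Section 3.2.1 excludes two or more MRI lesions of at least 5 mm and does not list multiple PET-CT lesions. Section 1 treats "2 or more focal bone marrow lesions detected by functional imaging including PET-CT" and/or MRI as myeloma-defining.

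The primary endpoint (13.1, 13.1.1), TTP (11.2.4.3, 13.1.2), PFS (11.2.5, 13.1.2) and duration of response (11.2.4.1, 13.1.2) speak of progression without citing 11.1.

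For the secondary response endpoint, the first FreeLite partial-response branch in 11.2.2.2 asks for a fall of at least 50% in the FLC difference that is also an absolute rise of at least 10 mg/dL. Both branches take the lowest response level as the reference.

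**The concern.** An endpoint criterion should not be one that the entry criteria allow a patient to have already. Section 11.1 drops the conditions that let certain patients in and does not say how a finding present at screening is scored. Its only protection is for calcium, renal function and anemia, which must be due to myeloma. Bone lesions and the MDEs carry no such condition.

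The primary result is a count compared with 24 of 39, so a few patients whose status depends on an unwritten rule can change the conclusion. In a single-arm trial that rule should be fixed before the outcomes are analysed.

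The FreeLite defect is of a different kind. A quantity cannot fall and rise at once, so the first branch can never be satisfied. It bears on the response rate, not on the primary endpoint.

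**Working it through.** **1. Who can meet a listed criterion at entry**

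| Finding at screening | Entry text | Section 11.1 |
|---|---|---|
| Light-chain smoldering disease, FLC ratio 100 or more | Allowed in the Summary, 2.4, 3.1.2 and 3.2.1 | Met |
| Ratio 100 or more, involved chain below 100 mg/L | Not excluded by 3.2.1 | Met |
| Marrow exactly 60% | Allowed by 3.1.2 and 3.2.1 | Met |
| Two or more MRI lesions, all under 5 mm | Not excluded by 3.2.1 | Met |

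The last three rows rest on section 3; the Summary is stricter. In rows 2 and 4 the patient needs another high-risk feature to qualify, because 3.1.2 counts only a ratio below 100, or a single MRI focal lesion (or diffuse change), as a qualifying feature.

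**2. The plan's own figures**

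Inputs from 13.1: n = 39, success if X ≥ 24, null rate 50%, target rate 70%, exact binomial.

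- Type I error: P(X ≥ 24 | 39, 0.5) = 0.0998, stated as 0.10.
- Power: P(X ≥ 24 | 39, 0.7) = 0.9056, stated as above 0.9.

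Both reproduce, so the design has no arithmetic error.

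**3. Patients scored as events at entry**

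Let k patients be so scored. They cannot contribute to the 24, so the chance of success is P(X ≥ 24 | 39 − k, p). The value of k is an assumption, because the documents give no expected number.

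| k | Power at 70% in the rest | Loss | Type I error at 50% |
|---|---|---|---|
| 0 | 0.906 | 0 | 0.100 |
| 1 | 0.863 | 0.043 | 0.072 |
| 2 | 0.807 | 0.098 | 0.049 |
| 3 | 0.737 | 0.169 | 0.033 |

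Losses are taken before rounding: for k = 1, 0.90559 − 0.86306 = 0.04253.

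**4. The opposite extreme**

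Suppose k patients could never have an event. The chance of success is then P(X ≥ 24 − k | 39 − k, p). At p = 0.5 this is 0.128, 0.162 or 0.203 for k = 1, 2 or 3. It is an upper bound, since such patients could still meet another 11.1 criterion. It shows that a blanket exemption pushes the count towards success.

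**The case against.** The strongest reply is that the intent can be recovered. Section 11.1 speaks of development and of disease that requires therapy, which points to new onset. Section 1 states the hypothesis that "early therapeutic interventions in patients with smoldering MM will prevent/delay progression to overt MM", and sections 5.5 to 5.7 tie stopping and follow-up to overt or active myeloma. On that reading nothing is lost, and no patient need be affected. This stands as far as intent goes. It does not supply a scoring rule for someone who has the finding at screening.

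Four stronger readings are tempting, and the documents do not support them.

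- *A single MDE is not enough.* The parenthesis might suggest that both a CRAB item and an MDE are needed. The same sentence says one of the listed criteria, the MDEs form one item of that list, 2.4 treats CRAB and other MDEs as alternatives, and section 1 regards the MDEs as requiring therapy in patients without symptoms. There is one sensible reading, and the wording is merely poor.
- *Biochemical progression is the primary event.* Section 11.2.2 does define progressive disease by laboratory change, and nothing in section 13 rules it out. But 1.3 and 5.1 let a patient with biochemical progression continue treatment, and 5.5 to 5.7 use overt or active disease. What is missing is a cross-reference, so no power loss is attached to this.
- *The trial risks a false positive.* Counting entry findings as events lowers type I error.
- *A finding present at screening should never count, however much it worsens.* The documents state no such rule. It would bear on when protocol therapy stops (5.5), and it moves the count towards success, as step 4 shows.

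**Conclusion.** The point holds as a gap between entry and endpoint wording, plus one row of response criteria that is wrong as written. Read literally, 11.1 makes some eligible patients events at entry; new onset is probably what was meant.

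The size is illustrative: a power loss of 0.043, 0.098 or 0.169 for 1, 2 or 3 affected patients, in the conservative direction. It assumes the planned 39 patients and cut-off of 24, a true rate of 70% in the others, and a number affected that the documents do not give and that may be zero. Section 1.1 records that accrual stopped in September 2017, and final enrolment is not stated, so these figures describe the design and not the trial as it ended.

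The change should be made: it concerns the primary endpoint and costs little. The missing citation of 11.1 and the parenthesis are clarifications. The FreeLite error affects the secondary response endpoint only.

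**What to change.** 1. **Entry and endpoint wording.** Reconcile the FLC, marrow and focal-lesion text (MRI and PET-CT) across the Summary and sections 1, 2.4, 3.1.2, 3.2.1 and 11.1, so that status at entry does not itself count as an event. The thresholds are for the sponsor to settle. In an amendment dated before outcome analysis, the sponsor should also specify how later worsening of a criterion met at screening is scored; this review does not choose that rule.
2. **Sensitivity analysis.** Because exempting such patients moves the count towards success, also report the primary result with them counted as events.
3. **Clarifications.** Cite 11.1 as the progression event for the primary endpoint, TTP and PFS. Say which definition applies to duration of response. Reword the parenthesis to agree with the requirement for one criterion.
4. **Response criteria (secondary endpoint only).** In the partial-response row of 11.2.2.2, remove the absolute-increase condition and measure the decrease from baseline. State the same reference in the FLC partial-response rule of 11.2.2.1, which names none.

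The cost is mainly wording. FLC and marrow are already on the screening calendar. If a lesion-size condition is kept, sizes may have to be read from the screening scans sent to the lead site, because the calendar does not say that they are recorded. The amendment would come after accrual closed, which is why the date and the sensitivity analysis matter.
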